6.7. Intervention After the End of the Study

No intervention will be provided to study participants at the end of the study.

7. DISCONTINUATION OF STUDY INTERVENTION AND PARTICIPANT DISCONTINUATION/WITHDRAWAL

7.1. Discontinuation of Study Intervention

This is a multiple dose study in which study participants may receive up to 42 days of dosing. In rare instances, it may be necessary for a participant to permanently discontinue investigational product. Discontinuation of dosing does not necessarily represent withdrawal from the study (see [Section 7.2](#)). If investigational product is permanently discontinued, the participant may remain in the study to be evaluated for the remainder of the study. At a minimum, an early termination visit will be conducted. See the [Schedule of Activities](#) for data to be collected at the time of intervention discontinuation (early termination) and follow-up and for any further evaluations that need to be completed. Additional follow-up may be required for safety evaluation, at the discretion of the investigator.

ECG Changes

A participant who meets either bulleted criterion based on the average of triplicate ECG readings will be withdrawn from the study.

- QTcF >500 msec.
- Change from baseline: QTcF >60 msec.

If a clinically significant finding is identified (including, but not limited to, changes from baseline in QTcF after enrollment), the investigator or qualified designee will determine if the participant can continue in the study and if any change in participant management is needed. This review of the ECG printed at the time of collection must be documented. Any new clinically relevant finding should be reported as an AE.

See the [SoA](#) for data to be collected at the time of intervention discontinuation and follow-up and for any further evaluations that need to be completed.

Adverse Events

Treatment will be discontinued and the participant withdrawn from the study for:

- Treatment-related serious adverse events (SAEs);
- Other serious or severe AEs, at the discretion of the investigator or sponsor.

Laboratory Abnormalities

All of the following laboratory abnormalities require discontinuation if they are confirmed:

- Hyperglycemia: see [Section 6.5.5](#);
- Creatine kinase >10 x ULN;

Note: Urine myoglobin and serum creatinine (SCr) will be performed as reflex testing for any participant with creatine kinase >10 x ULN.

- AST or ALT that meets ANY of the following:
 - >3 x ULN with at least one total bilirubin value >2 x ULN;
 - >3 x ULN accompanied by signs or symptoms consistent with hepatic injury [eg, new onset elevated prothrombin time/international normalized ratio (PT/INR)];
 - Two sequential AST or ALT elevations >5 x ULN, regardless of total bilirubin or accompanying signs or symptoms.

NOTE: See also [Appendix 6](#) for potential cases of drug-induced liver injury.

Potential Cases of Acute Kidney Injury

Abnormal values in serum creatinine (SCr) concurrent with presence or absence of increase in blood urea nitrogen (BUN) that meet the criteria below, in the absence of other causes of kidney injury, are considered potential cases of acute kidney injury and should be considered important medical events.

An increase of ≥ 0.3 mg/dL (or ≥ 26.5 μ mol/L) in SCr level relative to the participant's own baseline measurement should trigger another assessment of SCr as soon as practically feasible, preferably within 48 hours from awareness.

If the second assessment (after the first observations of ≥ 0.3 mg/dL [or ≥ 26.5 μ mol/L] in SCr relative to the participant's own baseline measurement) is ≥ 0.4 mg/dL (or ≥ 35.4 μ mol/L), the participant should be discontinued from the study and adequate, immediate, supportive measures taken to correct apparent acute kidney injury.

Participants should return to the investigator site and be evaluated as soon as possible, preferably within 48 hours from awareness of the second assessment confirming abnormal SCr result. This evaluation should include laboratory tests, detailed history, and physical assessment. In addition to repeating SCr, laboratory tests should include serum BUN, serum creatine kinase, and serum electrolytes (including at a minimum potassium, sodium, phosphate/phosphorus, and calcium), in addition to urinary dipstick, urine microscopic

examination, and urinary indices. All cases confirmed on repeat testing as meeting the laboratory criteria for acute kidney injury, with no other cause(s) of laboratory abnormalities identified, should be considered potential cases of drug-induced kidney injury irrespective of availability of all the results of the investigations performed to determine etiology of the abnormal SCr. If ≥ 2 healthy participants at a given dose level are noted to have 2 consecutive SCr results of ≥ 0.3 mg/dL (or ≥ 26.5 μ mol/L), an assessment of whether the finding may be considered an adverse drug reaction should be undertaken.

Prohibited Medications

Participants who are treated with any prohibited medication during the course of the study may require discontinuation. Participants who are administered or take a prohibited medication should be discussed with the sponsor for possible withdrawal from the study.

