7.2. Participant Discontinuation/Withdrawal From the Study

A participant may withdraw from the study at any time at his/her own request or may be withdrawn at any time at the discretion of the investigator for safety, behavioral, compliance, or administrative reasons.

At the time of discontinuing from the study, if possible, an early discontinuation visit should be conducted. See the [Schedule of Activities](#) for assessments to be collected at the time of study discontinuation and follow-up and for any further evaluations that need to be completed.

The early discontinuation visit applies only to participants who are randomized and then are prematurely withdrawn from the study. Participants should be questioned regarding their reason for withdrawal.

The participant will be permanently discontinued both from the study intervention and from the study at that time.

If a participant withdraws from the study, he/she may request destruction of any remaining samples, but data already generated from the samples will continue to be available, and may be used to protect the integrity of existing analyses. The investigator must document any such requests in the site study records.

If the participant withdraws from the study and also withdraws consent (see below) for disclosure of future information, no further evaluations should be performed and no additional data should be collected. The sponsor may retain and continue to use any data collected before such withdrawal of consent. When a participant withdraws from the study because of an SAE, the SAE must be recorded on the CRF and reported on the Clinical Trial (CT) SAE Report.

Lack of completion of all or any of the withdrawal/early termination procedures will not be viewed as protocol deviations so long as the participant's safety was preserved.

Withdrawal of Consent:

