Participants who request to discontinue receipt of study treatment will remain in the study and must continue to be followed for protocol-specified follow-up procedures. The only exception to this is when a participant specifically withdraws consent for any further contact with him or her or persons previously authorized by the participant to provide this information. Participants should notify the investigator in writing of the decision to withdraw consent from future follow-up, whenever possible. The withdrawal of consent should be explained in detail in the medical records by the investigator, as to whether the withdrawal is only from further receipt of investigational product or also from study procedures and/or posttreatment study follow-up, and entered on the appropriate CRF page. In the event that vital status (whether the participant is alive or dead) is being measured, publicly available information should be used to determine vital status only as appropriately directed in accordance with local law.

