8.3.1. Time Period and Frequency for Collecting AE and SAE Information

The time period for actively eliciting and collecting AEs and SAEs (“active collection period”) for each participant begins from the time the participant provides informed consent, which is obtained before the participant’s participation in the study (ie, before undergoing any study-related procedure and/or receiving investigational product), through and including a minimum of 28 calendar days after the last administration of the investigational product.

For participants who are screen failures, the active collection period ends when screen failure status is determined.

Medical occurrences that begin before the start of study intervention but after obtaining informed consent will be recorded on the Medical History/Current Medical Conditions section of the case report form (CRF), not the AE section.

Follow-up by the investigator continues throughout and after the active collection period and until the event or its sequelae resolve or stabilize at a level acceptable to the investigator, and Pfizer concurs with that assessment.

Investigators are not obligated to actively seek AE or SAE after conclusion of the study participation. However, if the investigator learns of any SAE, including a death, at any time after a participant has been discharged from the study, and he/she considers the event to be reasonably related to the study intervention or study participation, the investigator must promptly notify the sponsor.

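### Section 7.1 withdraws participants from the study for QTcF findings or treatment-related SAEs, in conflict with the follow-up set elsewhere, so recovery is least documented in those stopped for safety

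*Protocol*

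**What the plan says.** Protocol Section 7.1 opens by separating two events: "Discontinuation of dosing does not necessarily represent withdrawal from the study". It continues: "If investigational product is permanently discontinued, the participant may remain in the study to be evaluated for the remainder of the study", and then: "At a minimum, an early termination visit will be conducted".

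The same section then sets mandatory exits. Under ECG Changes, for a mean triplicate QTcF above 500 msec or a rise from baseline above 60 msec: "A participant who meets either bulleted criterion based on the average of triplicate ECG readings will be withdrawn from the study". The next paragraph leaves continuation after clinically significant findings, QTcF changes included, to the investigator. Under Adverse Events: "Treatment will be discontinued and the participant withdrawn from the study for" treatment-related SAEs, with other serious or severe events left to discretion.

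Section 7.2 states the effect of withdrawal: "The participant will be permanently discontinued both from the study intervention and from the study at that time". Further down, under Withdrawal of Consent, it says: "Participants who request to discontinue receipt of study treatment will remain in the study and must continue to be followed for protocol-specified follow-up procedures". Withdrawal of consent to contact is the only exception given there.

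Section 4.1 schedules an on-site visit and a later contact after the last dose for participants in all parts. Section 8.3.1 runs adverse-event collection for each participant "through and including a minimum of 28 calendar days after the last administration of the investigational product".

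**The concern.** Adverse events, safety laboratory tests, vital signs and ECGs are the primary endpoints (Protocol Section 3). Read literally, a participant who asks to stop dosing has a firmer claim to scheduled follow-up than one stopped for a QTcF above 500 msec or a drug-related SAE. Two sites could follow the same text and collect different data on such a participant. The gap falls in the off-drug period, when the study would learn whether the finding resolved.

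**Working it through.** The documents give no withdrawal rate and no figure that depends on this rule, so the check is a comparison of text with some simple arithmetic.

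**1. The scheduled follow-up.** Section 4.1 puts the on-site visit at last dose + 7 to 14 days and the contact at + 28 to 35 days.
- Part A, last dose Day 28: 28 + 7 = 35 and 28 + 14 = 42; 28 + 28 = 56 and 28 + 35 = 63. Table 1 has Days 35-42 and 56-63.
- Parts B and C, last dose Day 42: Days 49-56 and 70-77. Tables 3 and 5 agree.

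**2. The same rule for an early stop.** Suppose the last dose in Part A is Day 14. The on-site visit falls on Days 21-28 and the contact on Days 42-49. Under Section 8.3.1, adverse-event collection runs to at least Day 14 + 28 = Day 42. Under Section 7.2, participation ends at withdrawal. These cannot all apply as written.

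**3. Status after stopping, by reason.**

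| Reason | What the protocol says |
|---|---|
| Participant asks to stop | Stays in the study, must be followed (7.2) |
| QTcF criteria | Withdrawn from the study (7.1) |
| Treatment-related SAE | Treatment stopped and withdrawn from the study (7.1) |
| Other serious or severe AE | Same, at discretion (7.1) |
| Confirmed laboratory abnormality | Discontinuation required, without saying from what (7.1) |
| Potential kidney injury | Discontinued from the study, then asked back to the site for evaluation (7.1) |

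**4. The early-termination visit.** Section 7.1 makes it a minimum requirement. Section 7.2 asks for it only where possible, and does not count missed withdrawal procedures as deviations provided safety was preserved. Its ECG and vital signs are single readings (footnotes to Tables 1, 3 and 5), whereas the QTcF trigger and the time-matched baseline are triplicate averages.

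**5. What is kept and what is at risk.** Kept: membership of the safety set (anyone with at least 1 dose), the triggering value or event, and adverse-event follow-up. At risk: later scheduled ECGs, vital signs and laboratory tests, and the on-site visit.

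**6. Size.** One participant is 1/8 = 12.5% of the active group in Parts A and C, and 1/12 = 8.3% in Part B. The chance of at least one such withdrawal in a cohort is 1 - (1 - p)^n. The rates p below are assumptions:

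| Assumed p | n = 8 | n = 12 |
|---|---|---|
| 2% | 14.9% | 21.5% |
| 5% | 33.7% | 46.0% |
| 10% | 57.0% | 71.8% |

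**The case against.** The other side has a good case on consequences.

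**The safety data.** A reader might infer that these participants drop out of the primary safety data. They do not. Protocol Section 9.4.2 includes everyone dosed, and Section 9.4.2.1 tabulates each participant's maximum post-dose QTcF and maximum increase. SAP Section 6.1.1.7 counts planned and unplanned post-dose values. One of 8 with a rise above 60 msec is still reported as 12.5%.

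**Bias.** A reader might also infer that later cohort means are biased toward safety. The documents do not support a direction. Dosing stops in any case, so later values are off drug. With seven participants at an assumed 10 msec and the eighth at x, the mean is (70 + x)/8 if that person is kept and 10 if not. A persisting x = 65 gives 16.9; a return to x = 0 gives 8.75. Only the first would show bias toward safety, and it assumes the on-drug effect continues after dosing ends.

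**Existing safeguards.** Section 8.2.3 requires repeat ECGs at least hourly, with escalation if prolongation persists. Section 8.2.4 repeats clinically significant laboratory tests, and Section 8.3.3 follows events to resolution or stabilization. Sections 7.1 and 7.2 both point to the Schedule of Activities for data at discontinuation and follow-up. This stands, and it confines the loss to scheduled data. It does not close the gap: a rise above 60 msec that ends at or below 450 msec meets the withdrawal criterion but not the repeat-ECG trigger. A pointer to follow-up also does not settle whether someone already off the study attends it.

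**Wording.** The opening of Section 7.1 is permissive, so specific mandatory exits do not strictly contradict it. The must-be-followed rule is worded for people who ask to stop. Both points are fair. The conflicts with Sections 4.1 and 8.3.1, and over the early-termination visit, do not depend on them.

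**Conclusion.** The concern holds as a conflict between stated rules, and it should be fixed. Followed literally, Sections 7.1 and 7.2 end participation for people stopped on the QTcF criteria or for a treatment-related SAE, while Sections 4.1 and 8.3.1 presume that they are still being seen. The loss is limited to scheduled off-drug ECG, vital-sign and laboratory data and the on-site visit, so recovery is least well documented where a safety finding ended dosing. Each case is 12.5% of an active group of 8 or 8.3% of 12; how often it would occur is unknown. There is no hypothesis test (Section 9.1), and no sample size or error rate changes. The conclusion assumes that sites apply the withdrawal wording as written; a site that follows the pointers to the Schedule of Activities might lose little. No view is taken on the stopping criteria.

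**What to change.** Reconcile Protocol Sections 4.1, 7.1, 7.2 and 8.3.1 with the Schedule of Activities:
- Make stopping investigational product and leaving the study separate events, and say for each reason in Section 7.1 which of the two it triggers.
- Give the early-termination visit one status, and apply it and both existing follow-up contacts consistently to participants stopped for safety reasons, unless consent is withdrawn.
- Say how the investigator-discretion paragraph under ECG Changes relates to the two mandatory criteria.
- Leave the stopping criteria and thresholds untouched.

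In the SAP, identify values obtained after dosing stopped as off-drug. Sections 6.1.1.6 and 6.1.1.7 summarize by treatment, time and study-day window, with no visible rule to keep such values from being pooled unmarked into on-treatment cohort means.

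The cost is a few sentences in each document. The visits already exist, so the only added burden is attendance by the few participants affected.

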10.2. Appendix 2: Clinical Laboratory Tests

The following safety laboratory tests will be performed at times defined in the [Schedule of Activities](#). Additional laboratory results may be reported on these samples as a result of the method of analysis or the type of analyzer used by the clinical laboratory; or as derived from calculated values. These additional tests would not require additional collection of blood. Unscheduled clinical laboratory measurements may be obtained at any time during the study to assess any perceived safety concerns.

Investigators must document their review of each laboratory safety report.

Table 14. Protocol-Required Safety Laboratory Assessments

Hematology	Chemistry/Other	Urinalysis	At specified times
Hemoglobin	BUN/Urea	pH	At screening only:
Hematocrit	Serum Creatinine ^a	Glucose (qual)	• FSH ^c
RBC count	Plasma Glucose (fasting)	Protein (qual)	• Hepatitis B surface antigen (HbsAg)
MCV	Calcium	Blood (qual)	• Hepatitis C (HCV) antibody
MCH	Sodium	Ketones	• Hep B core antibody (HbcAb)
MCHC	Potassium	Nitrites	• Human immunodeficiency virus (HIV)
Platelet count	Chloride	Leukocyte esterase	
WBC count	Total CO ₂ (bicarbonate)	Urobilinogen	
Total neutrophils (Abs)	AST	Urine bilirubin	At times specified in the Schedule of Activities:
Eosinophils (Abs)	ALT	Microscopy ^b	• Urine drug screening ^e
Monocytes (Abs)	Total bilirubin		
Basophils (Abs)	Direct bilirubin		
Lymphocytes (Abs)	Indirect bilirubin		
	Alkaline phosphatase		
	Uric acid		
	Albumin		
	Total Bile Acids (TBA)		

Abbreviations: Abs = absolute; ALT = alanine aminotransferase; AST = aspartate aminotransferase; β -hCG = beta-human chorionic gonadotropin; BUN = blood urea nitrogen; CO₂ = carbon dioxide; FSH = follicle-stimulating hormone; MCH = mean corpuscular hemoglobin; MCHC = mean corpuscular hemoglobin concentration; MCV = mean corpuscular volume; qual = qualitative; RBC = red blood cell; WBC = white blood cell.

- a. Glomerular Filtration Rate (GFR) will be calculated using the modification of diet in renal disease (MDRD) equation:
$$\text{GFR (ml/min/1.73m}^2\text{)} = 175 \times \text{standardized Serum Creatinine-1.154} \times \text{age-0.203} \times 1.212$$

[if black] x 0.742 [if female].
- b. Only if urine dipstick is positive for blood, protein, nitrites, or leukocyte esterase.
- c. For confirmation of postmenopausal status in female participants only.
- d. [redacted]

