- e. The minimum requirement for drug screening includes cocaine, tetrahydrocannabinol (THC), opiates/opioids, benzodiazepines, and amphetamines (others are site and study specific).

Reflex testing may be conducted at investigator discretion; such tests may include PT/INR/partial thromboplastin time (PTT), myoglobin, creatine kinase.

In addition to the safety laboratory tests listed in the table above, blood samples will be collected and analyzed for additional tests as specified in the [Schedule of Activities](#).

All available results of the safety laboratory tests listed in the preceding table will be reviewed as part of dose escalation. Note that review of the following laboratory data is not required prior to dose escalation or progression to the next cohort/study part; results will be reviewed as they become available.

- CCI

[REDACTED]
TBA.

Laboratory/analyte results that could unblind the study **CCI** [REDACTED] will not be reported to investigator sites or other blinded personnel until the study has been unblinded; see also [Section 9.5](#).

CCI
[REDACTED]

10.3. Appendix 3: Adverse Events: Definitions and Procedures for Recording, Evaluating, Follow-up, and Reporting

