- For participants with baseline AST **OR** ALT **OR** TBili values above the ULN, the following threshold values are used in the definition mentioned above, as needed, depending on which values are above the ULN at baseline:
 - Preexisting AST or ALT baseline values above the normal range: AST or ALT values >2 times the baseline values AND $>3 \times$ ULN; or $>8 \times$ ULN (whichever is smaller).
 - Preexisting values of TBili above the normal range: TBili level increased from baseline value by an amount of at least $1 \times$ ULN **or** if the value reaches $>3 \times$ ULN (whichever is smaller).

Rises in AST/ALT and TBili separated by more than a few weeks should be assessed individually based on clinical judgment; any case where uncertainty remains as to whether it represents a potential Hy's law case should be reviewed with the sponsor.

The participant should return to the investigator site and be evaluated as soon as possible, preferably within 48 hours from awareness of the abnormal results. This evaluation should include laboratory tests, detailed history, and physical assessment.

In addition to repeating measurements of AST and ALT and TBili for suspected cases of Hy's law, additional laboratory tests should include albumin, creatine kinase (CK), direct and indirect bilirubin, gamma-glutamyl transferase (GGT), prothrombin time (PT)/international normalized ratio (INR), TBA, and alkaline phosphatase. Consideration should also be given to drawing a separate tube of clotted blood and an anticoagulated tube of blood for further testing, as needed, for further contemporaneous analyses at the time of the recognized initial abnormalities to determine etiology. A detailed history, including relevant information, such as review of ethanol, acetaminophen (either by itself or as a coformulated product in prescription or over-the-counter medications), recreational drug, supplement (herbal) use and consumption, family history, sexual history, travel history, history of contact with a jaundiced person, surgery, blood transfusion, history of liver or allergic disease, and potential occupational exposure to chemicals, should be collected. Further testing for acute hepatitis A, B, C, D, and E infection and liver imaging (eg, biliary tract) and collection of serum sample for acetaminophen drug and/or protein adduct levels may be warranted.

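### Dosing must stop for a confirmed creatine kinase above 10 x ULN, but no scheduled creatine kinase test is visible

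*Protocol*

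**What the plan says.** Protocol Section 7.1, under its laboratory heading, states: "All of the following laboratory abnormalities require discontinuation if they are confirmed". CK above 10 x ULN is one of the listed items. It stands alone, with no accompanying symptom or second abnormality required. A note to that item says that "Urine myoglobin and serum creatinine (SCr) will be performed as reflex testing for any participant with creatine kinase >10 x ULN".

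The footnotes to the Schedule of Activities send the reader to Appendix 2 for the content of the safety-laboratory row. There, Table 14 ("Protocol-Required Safety Laboratory Assessments") gives the panel. Its legible chemistry column does not list CK. Below the table, reflex testing is left to the investigator, and "such tests may include PT/INR/partial thromboplastin time (PTT), myoglobin, creatine kinase".

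CK is also directed in two work-ups. In the kidney-injury evaluation of Section 7.1, "laboratory tests should include serum BUN, serum creatine kinase, and serum electrolytes". For suspected Hy's law cases in Appendix 6, "additional laboratory tests should include albumin, creatine kinase (CK), direct and indirect bilirubin".

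**The concern.** A stopping threshold protects a participant only if the value is measured. Here the rule is unconditional, while every visible route to a CK result depends on a prior finding, someone's judgment or chance. A participant with an isolated, asymptomatic CK above the sponsor's own limit could continue daily dosing because nothing visible calls for the test.

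Section 4.2.4.1 describes this as the first repeated-dose study of the compound in humans, and dosing lasts up to 42 days. With no scheduled baseline, a CK obtained later for cause would also have no planned within-participant value to compare with. The visible nonclinical and clinical summaries report no muscle signal, so the point rests on the protocol's own rule and not on a known risk of the compound.

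**Working it through.** The plan gives no sample-size, power or event figure on this point, so the check sets the texts side by side.

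**1. The scheduled panel.** The legible chemistry entries of Table 14 are: BUN/urea, creatinine, fasting glucose, calcium, sodium, potassium, chloride, bicarbonate, AST, ALT, total bilirubin, direct bilirubin, indirect bilirubin, alkaline phosphatase, uric acid, albumin and total bile acids. That is 17 entries, none of them CK. No legible row of Schedule of Activities Tables 1 to 6 names CK either. Visible scheduled CK measurements: 0 in each of Parts A, B and C.

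**2. The other routes to a CK value.**

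| Route | What must come first | Reached by an isolated, silent rise? |
|---|---|---|
| Reflex test (Appendix 2) | Investigator's decision | Not by rule |
| Kidney work-up (Section 7.1) | Serum creatinine rise of at least 0.3 mg/dL, abnormal again on repeat | No |
| Liver work-up (Appendix 6) | Suspected Hy's law case | No |
| Unscheduled test (Appendix 2) | A perceived safety concern | No |
| Sponsor-specified extra sample (Section 8) | Sponsor's decision | Not visibly planned for CK |
| Incidental analyzer output (Appendix 2) | Depends on the laboratory's method | Not visibly planned for CK |

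On the fourth route the text is "Unscheduled clinical laboratory measurements may be obtained at any time during the study to assess any perceived safety concerns", and on the last it is "Additional laboratory results may be reported on these samples as a result of the method of analysis or the type of analyzer used". Both permit a CK result; neither plans one.

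**3. What the work-ups add.** A Hy's law case already meets the AST/ALT stopping rule. A repeat creatinine rise of 0.4 mg/dL or more already stops the participant. A repeat rise of 0.3 to below 0.4 mg/dL does not, so there the CK rule can add something.

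**4. Existing draws that could carry CK.** The detailed schedules place safety laboratories on Days -1, 14, 21 and 28 in Part A (Table 2), and on Days -1, 28 and 42 in Parts B and C (Tables 4 and 6). The overall schedules may show more draws, but their columns are broken in the text available.

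**5. Blood volume.** Section 8 plans about 535, 420 and 525 mL for Parts A, B and C, and caps the total at 550 mL in any 60 days when extra samples are added. Headroom: 550 - 535 = 15 mL (A), 550 - 420 = 130 mL (B), 550 - 525 = 25 mL (C). These are minimums, because the planned totals run over about 10 to 12 weeks. Existing tubes are therefore preferable to new draws in Parts A and C.

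**6. Room for lost participants.** Section 6.6.1 bases each escalation on data from at least 7 participants of the cohort. In a cohort of about 10 that leaves 10 - 7 = 3.

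**The case against.** The strongest reply is that this is a stated design. Appendix 2 assigns CK to for-cause testing, and Section 7.1 says what to do with a high value. That is coherent, and it stands: nothing here is a contradiction. It does not fully answer the point, because Section 7.1 neither limits the rule to CK measured for cause nor says which findings should prompt the test.

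Existing cover is also real. Participants stay in the unit throughout dosing, with adverse-event monitoring. AST, creatinine and dipstick blood are scheduled and may prompt a CK test. Strenuous exercise is barred for 48 hours before laboratory draws. What remains uncovered is a rise above 10 x ULN with no symptom and no prompting laboratory change. No visible text requires a CK test after a raised AST alone or after dipstick blood.

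Redaction is a fair caution. Table 14 footnote d and some blood-sampling rows are hidden. HbA1c and TSH are scheduled, and amylase and lipase are eligibility tests, yet none is legible in Table 14. Against this, the chemistry column shows no redaction marks, and Appendix 2 names CK as a discretionary reflex test. A hidden routine CK is unlikely but not excluded.

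Finally, routine testing has a price. Section 7.1 makes no exception for a cause other than the drug, so each confirmed elevation removes a participant from a small cohort. That is a true cost, but stopping at this threshold is the sponsor's own choice.

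**Conclusion.** The point holds as an inexpensive safety improvement. On the legible text, a mandatory stopping rule has no scheduled test behind it: 0 of 17 chemistry entries, and 0 visible scheduled CK measurements in any part. The conclusion assumes that the redacted material contains no routine CK. The documents give no basis for estimating how often a silent rise would occur.

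A reader might infer more than the documents support:

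- *That CK is the only laboratory stopping rule the schedule fails to serve.* The hyperglycemia rule in Section 6.5.5 needs fasting plasma glucose above 270 mg/dL on 3 consecutive measurements over 3 days. The Part A laboratory days in Table 2 cannot supply that sequence, and the visibly daily measurement is fingerstick glucose, which is different. Listing an analyte in Table 14 does not by itself make a rule workable.
- *That Part A participants would be titrated upward through an undetected rise and that the fix prevents this.* Default Part A titration takes up to about 2 weeks, and the first on-treatment laboratory day in Table 2 is Day 14. The first assured value would come near the end of titration.
- *That the number of CK tests the fix would create shows the size of the problem.* It measures workload, not risk, and any upper count depends on the broken columns of the overall schedules.

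**What to change.** Add CK to the Table 14 chemistry panel. Run it on existing samples at Day -1 and at each scheduled on-treatment safety-laboratory draw: at least Days 14, 21 and 28 in Part A, and Days 28 and 42 in Parts B and C. Keep the 10 x ULN threshold and the confirmation step.

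If routine CK is not wanted, the minimum is a sentence in Section 7.1 naming the findings that must trigger a CK test: muscle symptoms, a raised AST, dipstick blood, or a serum creatinine rise of at least 0.3 mg/dL. This lighter version would still miss a rise with no symptom and no prompting laboratory change.

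The full change costs one extra assay per existing tube, with no added visit or scheduled draw, and some confirmatory repeats. Its main downside is an occasional mandatory discontinuation for a CK rise not caused by the drug, in cohorts of about 10 where the escalation review needs at least 7 participants. Section 4.1 allows replacement of participants who discontinue, at the discretion of the investigator and sponsor, which softens that cost but may take time.
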